5.4. Dose Modification

Participants should adhere to the assigned dose. However, dose modification for management of adverse events should be considered as outlined below. Guidelines for reduction, interruption, or permanent discontinuation of study drug are provided below in Table 2 (study drug-related AEs) and Table 3 (study drug-related rash).

All instances of study drug modification (dose reduction, interruption, or discontinuation) are to be captured in the participants' medical record and on the CRFs. If the conditions/event leading to the dose modification have resolved, the original dose level may be resumed, unless in the judgment of the Investigator, this cannot be done safely.

If a participant enrolled in this study is on a reduced dose due to an AE prior to dose selection on GBT440-031, dosing may be continued at the reduced dose if deemed clinically appropriate by the Investigator.

Table 2. Dose Modification Guidelines for Study Drug-Related Adverse Events

Dose Reduction				
Event	Recommended Action			
Grade 2 or higher AE that is (1) study drug- related in the opinion of the Investigator AND (2) that precludes continued dosing at the current dose level due to safety concern or lack of tolerability (in the Investigator's judgment)	Study drug: May be reduced by one (1) tablet. If, in the opinion of the Investigator, a Grade 2 AE has resolved to ≤ Grade 1, participant may resume study drug at the original dose. If, in the opinion of the Investigator, the AE poses a significant safety concern such that a dose hold is considered, the Investigator may consider a dose interruption (hold), Maximum dose hold is 5 continuous days. If, in the opinion of the Investigator, a longer dose hold is clinically needed, the Medical Monitor should be contacted for discussion.			
ALT ≥3x ULN if ALT WNL at baseline OR >3X ULN AND a ≥2-fold increase above baseline values if elevated ALT values at baseline In the absence of additional signs of compromised liver function such as elevated	Study drug: Confirm by repeat testing within 48 to 72 hours if possible, then repeat liver panel at least weekly until ALT levels improves. Additional Actions: If ALT levels continue to increase reduce by one tablet and notify the Medical Monitor			

Table 2. Dose Modification Guidelines for Study Drug-Related Adverse Events

Dose Reduction	
Event	Recommended Action
PT, PTT, INR, elevated conjugated bilirubin, jaundice, or hepatic pain.	

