7. ASSESSMENT OF SAFETY

7.1. Safety Parameters

Participant safety and tolerability will be monitored during the study using standard measures, including physical examinations, vital signs (including blood pressure [BP]), safety laboratory tests, concomitant medication usage and AE monitoring. Assessments will be performed at defined times during the study as indicated in the Schedule of Assessments (Appendix 1).

There are additional assessments (Week 4 and Week 8) during the first 8 weeks of this study for participants who transition from GBT440-031 and meet the following criteria:

- If the dose for this trial is 1500 mg, and the participant was randomized to either voxelotor 900 mg or placebo in GBT440-031.
- If the dose is 900 mg, and the participant was randomized to placebo in GBT440-031 study.
- If a participant received less than 12 weeks of treatment in GBT440-031.

More frequent assessments, as per Investigator or health care provider judgement, may be conducted if needed for management of AEs or per standard of care at each site.

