7.1.5. Laboratory Assessments

Central laboratory assessments will be performed for participants enrolled in the United States and Europe.

Local laboratory assessments will be performed by each site's local laboratory for participants enrolled outside of the United States or Europe.

The laboratory parameters listed in the sections below will be assessed. Additional laboratory assessments may be collected as indicated per standard of care for clinical management.

For adolescent participants, the total volume of blood collected for will not exceed the recommended blood sample volume limits outlined in 2010 WHO Guidelines. For this study, 12 years of age is the youngest age to be enrolled, thus total blood volume collection will not exceed 2.4 mL/kg in a given 4 week period, for any adolescent enrolled in the study.

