#### 3.2. Visit Windows

For summaries by timepoint (e.g., laboratory values and vital signs), analysis visit windows will be used to classify assessments based on the actual treatment day of the measurement regardless of the original nominal visit label. This includes assessments collected at Unscheduled or EOS visits. Target study days, the protocol-specified study day windows, and the analysis visit windows are shown in Table 1.

**Table 1:** Analysis Windows

Timepoint	Target Study Day (relative to first dose)	Visit Window per Protocol (treatment days)	Window for Statistical Analysis (treatment days)
Baseline	1		Last value a taken on or prior to date of first dose in GBT440-034
Week 4	28	[23, 33]	[2, 42]
Week 8	56	[51, 61]	[43, 70]

Timepoint	Target Study Day (relative to first dose)	Visit Window per Protocol (treatment days)	Window for Statistical Analysis (treatment days)		
Week 12	84	[79, 89]	[71, 126]		
Week 24	168	[158, 178]	[127, 252]		
Week 48	336	[326, 346]	[253, 420]		
Week 72	504	[494, 514]	[421, 588]		
Week 96	672	[662, 682]	[589, 756]		
Week 120	840	[830, 850]	[757, 924]		
Week 144	1008	[998, 1018]	[925, 1092]		
Week 168	1176	[1166, 1186]	[1093, 1260]		
Week 192	1344	[1334, 1354]	[1261, 1428]		
	< Continues with 24-week intervals >				

Note: If multiple measurements fall within the statistical analysis window, the average of the measurements will be used.

Note that per the protocol Schedule of Assessments, laboratory assessments and vital signs are collected at visits up to Week 48. After Week 48, laboratory assessments are collected per standard of care for clinical management with the following exception: for participants enrolled outside of the US and Europe, hemoglobin and clinical measures of hemolysis (% reticulocytes, absolute reticulocytes, and bilirubin [total, direct, and indirect]) are collected after Week 48 at 24-week intervals (see Section 5.4.3).

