# 5.5. Treatment Effect (Durability of Hematologic Effect)

Descriptive summaries of hemoglobin, indirect bilirubin, % reticulocytes, and absolute reticulocytes for all participants at GBT440-034 baseline and each evaluation post baseline through Week 48, as well as changes from baseline over time, will be provided. Laboratory assessments within 8 weeks post RBC transfusion, for any reason, will be imputed by the last laboratory value prior to the transfusion.

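### Averaging every value in the wide SAP 3.2 windows lets event-driven and off-drug samples into the Week 12, 24 and 48 durability summaries

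*SAP*

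**What the plan says.** SAP 3.2 sets one rule for all summaries by timepoint: "analysis visit windows will be used to classify assessments based on the actual treatment day of the measurement regardless of the original nominal visit label". It adds "This includes assessments collected at Unscheduled or EOS visits", and the note to Table 1 says "If multiple measurements fall within the statistical analysis window, the average of the measurements will be used". Scheduled values get no priority, and no scheduled-only summary is planned.

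SAP 5.5 is such a summary: "Descriptive summaries of hemoglobin, indirect bilirubin, % reticulocytes, and absolute reticulocytes for all participants at GBT440-034 baseline", and then at each evaluation through Week 48 with changes from baseline. It has one event-related rule. Values within 8 weeks after a red cell transfusion are replaced by the last value before it. The SAP does not say whether this happens before or after averaging.

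On extra samples, Protocol 7.1 says "More frequent assessments, as per Investigator or health care provider judgement, may be conducted if needed for management of AEs" or under site standard of care, and Protocol 7.1.5 says "Additional laboratory assessments may be collected as indicated per standard of care for clinical management". Protocol 4.3 and Appendix 1 put the EOS visit of early withdrawals 28 to 35 days after the last dose. Appendix 1 includes hematology and chemistry at that visit.

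Baseline is described in two ways. The Table 1 row takes the last value on or before the first dose. SAP 3.1 also starts from the last available value, but then averages all pre-dose laboratory records if the extension database holds more than one.

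**The concern.** The number of values averaged for a participant can depend on that participant's clinical course. Someone seen only at scheduled visits contributes a scheduled value. Someone bled several times in an acute episode contributes an average in which the scheduled value is a minority. Someone who stopped drug early can contribute a value taken about a month off treatment. SAP 5.5 is meant to describe hemoglobin and hemolysis on voxelotor, so both kinds of value can blur it.

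Results are also shown by prior treatment group (SAP 4.2). If the frequency of extra sampling or early stopping differed between groups, the group summaries would differ partly for that reason. All analyses are descriptive, so the summarised means are themselves the result.

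**Working it through.** **1. Window lengths.** Table 1 boundaries are midpoints between target days: (84+168)/2 = 126, (168+336)/2 = 252, (336+504)/2 = 420. The stated windows reproduce exactly.

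| Visit | Analysis window (days) | Length | Protocol window (days) | Length | Ratio |
|---|---|---|---|---|---|
| Week 12 | 71 to 126 | 56 | 79 to 89 | 11 | 5.1 |
| Week 24 | 127 to 252 | 126 | 158 to 178 | 21 | 6.0 |
| Week 48 | 253 to 420 | 168 | 326 to 346 | 21 | 8.0 |

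**2. Off-drug values.** With a last dose on Day 200, an early-withdrawal EOS visit falls between Day 200+28 = 228 and Day 200+35 = 235. That is inside the Week 24 window, so the value is averaged with any on-drug value there.

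**3. Size of an event-driven shift.** The documents give no count of unscheduled hemoglobin samples and no values for them, so the inputs are assumptions:

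- *f*: share of participants with event samples in the window, 10% to 20%
- *k*: such samples per affected participant, beside one scheduled value, 1 to 3
- *d*: how far those samples lie below the scheduled value, 1 to 2 g/dL

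Shift for an affected participant = -d × k/(k+1). Shift in the cohort mean = -f × d × k/(k+1).

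| f | k | d (g/dL) | Participant shift | Cohort shift |
|---|---|---|---|---|
| 10% | 1 | 1 | -0.50 | -0.05 |
| 20% | 1 | 1 | -0.50 | -0.10 |
| 20% | 3 | 2 | -1.50 | -0.30 |
| 20% | 1 | -0.5 (event samples higher) | +0.25 | +0.05 |

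For scale, Protocol 1.3.2 describes the parent-study effect as more than 1 g/dL against placebo at 24 weeks. Each participant supplies one value per window, so frequent sampling does not add weight in the cohort mean. The distortion is within participant.

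**4. Transfusion rule.** These figures are before that rule. It removes post-transfusion values but can repeat a low one. Take a scheduled value of 10, a pre-transfusion value of 8, and a follow-up value imputed as 8. If imputation comes before averaging, the visit value is (10+8+8)/3 = 8.67. Selecting one value per window does not remove this: a scheduled value within 8 weeks of transfusion is still overwritten. If a share *t* of participants is affected, the remaining shift is up to t × d, for example 5% × 1 = 0.05 or 20% × 2 = 0.40 g/dL.

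**5. Baseline.** Under SAP 3.1 averaging can apply at baseline too, and could partly offset a post-baseline shift in the change score. Under the Table 1 row it cannot. The size of any net effect therefore depends on which rule is followed.

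**The case against.** The strongest reply is that the average is a legitimate choice. The aim is durability and trend over treatment, and nothing defines the target as hemoglobin when well. Taking only scheduled values could discard genuine declines. No tests are planned, and a downward shift would understate benefit. Interim open-label data have already been summarised (SAP 2.4), so changing the rule now is a data-aware choice and may break comparability.

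Part of this stands. Comparability is a good reason to keep the all-values average as a sensitivity summary. But a plain mean of all draws is not the average level over the window, because it weights by draws and not by time. Suppose a participant is at 10.0 g/dL for 161 days and 8.0 for 7 days of the Week 48 window, with one scheduled draw at 10.0 and three at 8.0. The rule gives (10+24)/4 = 8.5, while the time average is (161×10 + 7×8)/168 = 9.92. Being descriptive or conservative does not make the summarised value right, and neither argument justifies putting an off-drug value into an on-drug summary.

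A reader might infer three stronger points that the documents do not support:

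- **Hemoglobin is pulled down and the result is biased.** The direction is unknown. Standard-of-care samples need not be illness samples, and the repeats prescribed after an ALT rise ("then repeat liver panel at least weekly until ALT levels improves", Protocol 5.4) are liver panels, with hemoglobin not named.
- **A single baseline value is always compared with an average.** SAP 3.1 provides for an averaged baseline when several records exist.
- **ALT peaks are hidden.** This is largely covered. SAP 5.3.3 uses all assessments for maximum grade up to Week 48 (central laboratory values), clinically significant abnormalities are recorded as adverse events, and Protocol 8.1.1.1 flags out-of-range values in listings.

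**Conclusion.** The point holds in conditional form. The SAP lets event-driven and off-drug values into the SAP 5.5 visit averages with no priority for scheduled on-treatment values, and its windows are 5 to 8 times as wide as the protocol's at Weeks 12, 24 and 48. The summaries may be distorted. Whether they are, and in which direction, cannot be told from the documents. Under the stated assumptions the event-driven shift runs from negligible (-0.05 g/dL) to material (-0.30 g/dL) against a reference effect of more than 1 g/dL. It would be upward if event samples ran higher. The inclusion of off-drug EOS values needs no assumption about sampling behaviour, only an early withdrawal whose EOS visit falls in a window; its size is also unknown. This is an inexpensive improvement to the plan and not a flaw that invalidates it.

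**What to change.** For SAP 5.5:

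- Use the scheduled on-treatment value nearest the target day. Use the nearest on-treatment unscheduled value only when the window holds no scheduled one.
- Exclude values taken after treatment has stopped, such as early-withdrawal EOS values. This must be explicit, because EOS is itself a scheduled visit and a nearest-scheduled rule alone could select it.
- State whether transfusion imputation comes before value selection, and whether the value carried forward may be an unscheduled one.
- Reconcile the baseline averaging sentence in SAP 3.1 with the baseline row of Table 1.
- Keep all values for the maximum-grade tables and listings.
- Show the all-values average as a sensitivity summary, with counts of unscheduled values per window, for comparability with earlier interim summaries.

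The cost is a few SAP sentences, a record-selection flag and one extra summary. A single value is slightly noisier than an average. Because open-label data have already been seen, the change should be recorded as made after the interim summaries.

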## 4. ANALYSIS POPULATIONS

# 4.1. Enrolled Population

All participants with signed informed consent will be considered enrolled in the study.

Enrollment by country and study site, subject disposition, and protocol deviations will be summarized for the enrolled population.

# **4.2.** Safety Population

The safety population includes all enrolled participants who received treatment with study drug (voxelotor) during Study GBT440-034.

The safety population will be the primary analysis population for this study.

Analyses will be presented for overall population, and by prior treatment group (i.e., placebo, voxelotor 900 mg, and voxelotor 1500 mg) based on treatment received in the parent study GBT440-031, as appropriate.

<sup>a Including Week 72, End of Treatment, or End of Study laboratory values collected in Study GBT440-031.

#### 5. STATISTICAL METHODS

All statistical analyses will be descriptive in nature; no formal statistical tests are planned.

# **5.1.** Summaries of Study Conduct

The number of participants enrolled will be tabulated by country and study site. Participant disposition (the number of participants treated, discontinuing the study early, and completing the study) will be tabulated. Reasons for early study drug discontinuation and study discontinuation will be summarized.

Any eligibility criteria deviations, other important protocol deviations (i.e, those categorized as 'critical' in severity), and protocol deviations related to COVID-19 will be tabulated and evaluated for potential impact on the interpretation of study results. Medication errors (e.g., administration of incorrect dosage or administration of expired study drug) per protocol amendment 3.0 (protocol Section 7.5) will be listed.

# 5.2. Summaries of Demographic and Baseline Characteristics, Medical History, and Concomitant Medications

Demographic and baseline characteristics (such as age at GBT440-034 enrollment, sex, race, ethnicity, sickle cell genotype, hydroxyurea (HU) use at GBT440-034 enrollment, and geographic region) will be summarized for the safety population.

Medical history will be coded using Medical Dictionary for Regulatory Activities (MedDRA) and summarized. Prior and concomitant medications will be coded using the World Health Organization (WHO) Drug Dictionary and summarized. For both MedDRA and WHO Drug Dictionary, the most current version at the time of analysis will be used.

Time on study, defined as time from informed consent date to the participant's end of study date, will also be tabulated.

# 5.3. Safety Analyses

Safety will be assessed through descriptive summaries of adverse events, clinical laboratory test results, electrocardiogram (ECG) findings, and vital signs. Safety summaries will be based on the safety population (Section 4.2).

## **5.3.1.** Exposure to Study Drug and Adherence

Duration of exposure is defined based on the difference between the dates of the first and last dose of study drug, i.e.,

$$Duration of \ Exposure \ (weeks) = \frac{LastDoseDate - FirstDoseDate + 1}{7}$$

and will be summarized descriptively.

For each participant, the study drug adherence will be calculated based on the ratio of the number of tablets taken on study to the expected number of tablets from the first to the last dose date:

Study Drug Adherence (%) = 
$$100 \times \frac{Number\ of\ Tablets\ Taken}{Expected\ Number\ of\ Tablets}$$

Study drug adherence will be summarized descriptively.

In addition, the number of dose reductions per participant and the number of dose interruptions per participant will be summarized.

The number and percent of participants who transitioned from five tablets of voxelotor 300 mg daily to three tablets of voxelotor 500 mg daily during the study will be tabulated.

#### **5.3.2.** Adverse Events

Adverse events will be classified according to MedDRA; the most current version at the time of analysis will be used. Severity of adverse events will be graded using the National Cancer Institute Common Terminology Criteria for Adverse Events (NCI CTCAE) version 4.03, when possible, or based on the protocol-specified grading for adverse events not covered in the NCI CTCAE.

Non-SCD-related adverse events and SCD-related adverse events will be summarized separately. SCD-related adverse events include sickle cell anaemia with crisis, acute chest syndrome, pneumonia, priapism, and osteonecrosis. All other adverse events will be considered non-SCD-related.

Summaries of TEAEs, defined as adverse events with an onset on or after the date of informed consent until 28 days after last dose of study drug, will be tabulated by MedDRA system organ class (SOC) and preferred term, as appropriate.

Summaries of TEAEs will be provided for the following categories:

- Non-SCD-related TEAEs
- Non-SCD-related TEAEs by study year
- Non-SCD-related TEAEs by maximum severity
- Non-SCD-related TEAEs assessed as related to study drug by the investigator
- Non-SCD-related TEAEs of rash (group term)
- Non-SCD-related TEAE of abdominal pain (group term)
- Non-SCD-related treatment-emergent serious adverse events (SAEs)
- Non-SCD-related treatment-emergent SAEs by study year
- Non-SCD-related treatment-emergent SAEs assessed as related to study drug by the investigator
- SCD-related TEAEs
- SCD-related TEAEs by study year
- SCD-related TEAEs by maximum severity
- SCD-related TEAEs assessed as related to study drug by the investigator

- SCD-related treatment-emergent SAEs
- SCD-related treatment-emergent SAEs by study year
- SCD-related treatment-emergent SAEs assessed as related to study drug by the investigator
- All TEAEs leading to study drug discontinuation
- All TEAEs leading to study drug dose modification (dose reduction or interruption)

Listings for all adverse events, adverse events leading to study drug discontinuation, SAEs, and deaths will be provided.

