8.1.1. Study Endpoints

8.1.1.1. Safety

Safety data analysis will be performed on all participants enrolled in the study.

A treatment-emergent adverse event (TEAE) is defined as an AE that emerges on or after initiation of study drug (having been absent pretreatment), or an AE that existed pretreatment and worsened on treatment (relative to the pretreatment state). The incidence of TEAEs will be tabulated by system organ class (SOC), preferred term, severity and relationship to study drug. AEs considered to be related by the Investigator will be summarized. AEs will be reported by severity and relatedness to study treatment and classified via the Medical Dictionary for Regulatory Activities (MedDRA).

Changes in clinical laboratory data (hematology, serum chemistry, will be summarized.

For the laboratory safety data, out of range values will be flagged in the data listings and a list of clinically significantly abnormal values will be presented.

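### SAP 5.3.2 commits to no pooled any-TEAE or any-SAE table and no death table: 16 of its 18 named summaries cover either non-SCD-related or SCD-related events alone

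*SAP*

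**What the plan says.** SAP 5.3.2 (Adverse Events) sets the rule: "Non-SCD-related adverse events and SCD-related adverse events will be summarized separately". It defines the first group by five terms: "SCD-related adverse events include sickle cell anaemia with crisis, acute chest syndrome, pneumonia, priapism, and osteonecrosis". The second group is the remainder: "All other adverse events will be considered non-SCD-related".

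The section then names 18 categories of TEAE summary:

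- nine restricted to non-SCD-related events;
- seven restricted to SCD-related events;
- two unrestricted: "All TEAEs leading to study drug discontinuation" and the matching summary for dose modification.

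The severity, relatedness, study-year and SAE summaries are all in the first two groups, for example "Non-SCD-related TEAEs by maximum severity". SAEs as a whole and deaths are covered by this sentence: "Listings for all adverse events, adverse events leading to study drug discontinuation, SAEs, and deaths will be provided".

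Protocol 8.1.1.1 (Safety) has no such split: "The incidence of TEAEs will be tabulated by system organ class (SOC), preferred term, severity and relationship to study drug". SAP section 2 says that the SAP prevails where the two documents differ. SAP 4.2 plans results for the whole safety population and by prior treatment group, as appropriate. SAP section 6 leaves the table mockups to a separate document.

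**The concern.** Long-term safety is the first parameter under the study objective (Protocol section 2). The trial is open-label with no formal tests (SAP section 5), so descriptive incidence figures are the safety result. A reader of the final report will expect to see what share of participants had any TEAE, any SAE, any related SAE or a fatal event, overall and by prior treatment. As SAP 5.3.2 is written, no planned table answers those questions. Two tables that each give part of the answer do not combine into the whole when the same participant can appear in both.

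The line between the halves also differs within the SAP. Section 5.4.1 lists twelve SCD-related complications, and section 5.3.2 counts only five of them as SCD-related. The other seven (hepatic sequestration, leg ulcers, pulmonary hypertension, retinopathy, scleral icterus, splenic sequestration and stroke) therefore fall in the non-SCD half of the adverse event tables. Pooled totals would not depend on where that line is drawn.

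**Working it through.** The plan states no figure on this point, so there is none to reproduce. The check has three steps.

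**1. Protocol 8.1.1.1 against SAP 5.3.2**

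| Item | Protocol 8.1.1.1 | SAP 5.3.2 |
|---|---|---|
| TEAEs by preferred term | Yes, no split | Yes; each term lies in exactly one half, so nothing is lost |
| TEAEs by SOC | Yes, no split | Within each half; no pooled total for a SOC with terms in both |
| TEAEs by severity | Yes, no split | Maximum severity within each half only |
| TEAEs by relationship | Yes, no split | Related TEAEs within each half only |
| Any SAE, any related SAE | Not expressly required | Within each half; pooled only as a listing |
| Deaths | Not expressly required | Listing only |
| TEAEs leading to discontinuation or dose modification | Not mentioned | Pooled |

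Of the 18 summaries, 9 + 7 = 16 are confined to one half and 2 are pooled. As an example of the SOC row, if pneumonia (SCD half) and upper respiratory tract infection (non-SCD half) code to the same SOC, no planned table gives the share of participants with any event in that SOC.

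**2. What the halves imply for the total**

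The halves are exclusive and exhaustive by event, but not by participant. Let pA be the share with a non-SCD-related event and pB the share with an SCD-related event. Then

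max(pA, pB) ≤ overall share ≤ min(1, pA + pB),

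and, if the two were independent, overall share = 1 − (1 − pA)(1 − pB).

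When pA + pB is at most 1, the width of the range equals the smaller of the two shares.

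**3. Illustration**

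Input from the documents: a ceiling of 274 participants (SAP 2.3). The actual safety population is not given. The shares below are assumptions, because the documents give no event rates.

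| Event | pA | pB | Overall range | If independent | People, at 274 |
|---|---|---|---|---|---|
| SAE | 10% | 15% | 15% to 25% | 23.5% | 41 to 68 |
| SAE | 20% | 40% | 40% to 60% | 52% | 110 to 164 |
| SAE | 30% | 50% | 50% to 80% | 65% | 137 to 219 |
| TEAE | 90% | 70% | 90% to 100% | 97% | 247 to 274 |

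Third row worked: max(0.30, 0.50) = 0.50; 0.30 + 0.50 = 0.80; 1 − 0.70 × 0.50 = 0.65; 0.50 × 274 = 137; 0.80 × 274 = 219.2.

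Across the assumed SAE shares, the split tables leave the overall figure open by 10 to 30 percentage points. The same bounds apply within each prior treatment group.

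**The case against.** The best defence has four parts.

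First, the information is not lost. The SAE and death listings are pooled, and SAP 5.1 tabulates the number treated, so anyone can count. Fatal TEAEs should also show as Grade 5 in the two maximum-severity tables. This stands in part. A reader might infer that the report could not state how many participants had an SAE or died, and the documents do not support that. But a hand count is not a planned result, and a death outside the TEAE window would not appear in the severity tables.

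Second, the protocol is largely met. SAP 5.3.2 covers SOC, preferred term, severity and relationship, and the precedence rule settles any difference. This also stands in part. It would be too strong to call the SAE and death omissions a breach of Protocol 8.1.1.1, which asks for neither table. What differs is the pooled TEAE breakdown by SOC, severity and relationship. The precedence rule makes that difference effective but gives no reason for it.

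Third, the mockups may contain an overview table. They cannot be seen here, so its absence from them cannot be shown. They are described as supporting the analyses in the SAP, however, and the SAP proposes no such table.

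Fourth, the split is sensible. Under Protocol 7.2.2.5 SCD complications are recorded as AEs only when judged to have worsened or changed in nature, so pooled rows mix two recording rules, and frequent disease events could hide other signals. This is a good reason to keep the split tables, but not to omit the totals. A reader might go the other way and infer that the split dilutes a safety signal. Nothing in the documents shows this, and no preferred term is divided.

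**Conclusion.** The point holds in a limited form. Apart from the two pooled summaries, SAP 5.3.2 commits to no table giving the share of participants with any TEAE, any SAE, any related TEAE or SAE, or a given worst grade, and it commits to no death table. These totals cannot be derived from the split tables. They are bounded only by the larger half and the sum of the halves. The size depends on event rates that the documents do not give; the 10 to 30 percentage points for SAEs rest on assumed shares. Term-level incidence is intact, the listings allow SAE and death counts by hand, and the unseen mockups may already include an overview. It should be corrected, because the missing totals are headline results for a long-term safety study, but it does not threaten the data or the validity of the tables that are planned.

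**What to change.** Add to SAP 5.3.2, for the safety population, overall and by prior treatment group, counting each participant once:

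1. One pooled overview with n and % for any TEAE, any related TEAE, maximum grade, any treatment-emergent SAE, any related treatment-emergent SAE, fatal TEAEs, and all deaths.
2. Pooled TEAE tables by SOC and preferred term, by severity and by relationship, as in Protocol 8.1.1.1.

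Keep the split tables and state why they are shown. A death rate per 100 person-years with a confidence interval is optional; neither document calls for it.

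The cost is a short SAP change and a few extra tables from adverse event data already collected. The drawback is that pooled rows mix disease-related and other events, which is why the split tables stay beside them.
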